8.1 Statistical and Analytical Plans

The approach to sample size and statistical analyses are summarized below.

8.2 Statistical Hypotheses

The primary outcome for this study is graft failure by 12 months. The null/alternative hypotheses are:

- Null Hypothesis:* There is no difference in the probability of graft failure by 12 months between the diabetic group and the non-diabetic group.
- Alternative Hypothesis:* The probability of graft failure by 12 months is different for the diabetic and non-diabetic groups.

- A participant can enroll both eyes into the study, if both are eligible. It is anticipated that about 30% of participants will have two study eyes, based on the CPTS data⁵⁴, data from single site study of Price et al for DMEK⁵⁵, and a participating surgeon survey, indicating more common bilateral cases associated with DMEK, the endothelial keratoplasty procedure in the DEKS, compared to DSAEK which was the procedure in the CPTS. This would mean it is expected that approximately **1092 participants would need to be enrolled in order to enroll 1420 study eyes**.

Although both eyes of a study participant can be enrolled, and/or both eyes of the donor may be provided for the study, the sample size calculation does not adjust for these correlations, for the reasons noted below.

- If participants with two study eyes receive a cornea from a donor with known diabetes for the first eye, the second eye will receive a cornea from a donor without known diabetes. If the first study eye received a cornea from a donor without known diabetes, then there is a 1/3 chance that the second study eye will receive a cornea from a donor with known diabetes. Note, the primary analyses will adjust for these correlations. Those classified as having *known diabetes* are participants with a diabetes diagnosis prior to tissue donation or reclassified as diabetic based on post-mortem HbA1c values.

Regarding donors, CPTS found there were no cases of graft failures occurring from the cornea mates of the same donor because of the low graft failure rate and low number of cornea mates in the study;³⁵ a similar trend is expected in the DEKS and sample size will not be adjusted for this. If there are cases of graft failures occurring from cornea mates both assigned in the study, sensitivity analysis will account for the correlation in the models.

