Study eye eligibility is determined at the time DMEK surgery is scheduled. A participant can contribute two study eyes if both eyes are eligible. The eligibility of the second eye, if applicable, will be assessed at the time surgery on the second eye is scheduled; second eye surgery as part of the study can be performed between 7 days and 6 months (182 days) after DMEK on the first eye. If participant agrees to second eye study participation, he/she will not receive a cornea from a donor with known diabetes in both study eyes. Specifically, if the first eye received a cornea from a donor with known diabetes, after thorough medical record review as part of standard eye banking practices (see Section 3.2.2), the second eye will receive a cornea from a donor without known diabetes. (Study surgery could thus potentially be cancelled if a donor cornea without known diabetes is not available). If the first eye received a cornea from a donor without known diabetes, the second eye will proceed through the minimization algorithm for assignment of donor tissue. Note, because of the reclassification process based on HbA1c testing at the central laboratory, this means that donors not known to have diabetes after thorough eye bank staff medical record review, may still have diabetes that was not known at the time of the keratoplasty procedure. This testing is not standard practice and could delay proceeding with the keratoplasty if the cornea could not be placed until the result (HbA1c value < or \geq 6.5%) was returned. Therefore, there is a possibility that a participant who agreed to both eyes participating in the study can in both eyes receive a cornea from a donor classified as having diabetes based upon post-mortem study-specific HbA1c laboratory values (\geq 6.5%) that are not acquired in standard practice.

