3.2.1 Donor Cornea Tissue Suitability

1. All eye banks will follow their procedural routine for procurement of cornea tissue and determination of suitability for DMEK in accordance with the Medical Standards and Procedure Manual of the EBAA. This includes standard serologic testing, specular microscopy, and slit lamp examination.

2. The following eligibility criteria will apply to all donor cornea tissue assigned to study eyes.

- Must meet current EBAA standards for human corneal transplantation
- Age of donor at time of death 50–75 years
- If the donor body was refrigerated or eyes on ice within 12 hours of death, the body or eye may stay refrigerated up to 24 hrs; if no refrigeration then the death to preservation time should be <12 hrs
- Preservation time ≤ 11 days
- Eye bank determined minimum ECD (at screening) of ≥ 2300 cells/mm²
- Pleomorphism/Polymegethism: At eye bank and medical director discretion

- Guttae: no true guttae present
- No evidence of central endothelial cell damage/trauma or dystrophy, such as FECD, by slit lamp examination

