8.7 Analysis of the Secondary Endpoint

For ECD, only participants with a gradable 1-year image who have not experienced graft failure 1-year after DMEK will be included in the analysis. There will be no imputation of missing data. Summary statistics (mean \pm SD or median (IQR)) appropriate to the distribution will be tabulated by donor diabetes status group and at baseline, 1-year and for the changes from baseline to 1-year.

Repeated measures regression models with unstructured covariance including data from baseline, 1 month, and 1 year will be used to compare donor diabetes status effects while adjusting for baseline ECD, corneal diagnosis, and recipient study eyes (random effect. A point estimate, 95% confidence interval, and two-sided p-value will be reported for the donor diabetes status effect based on the linear regression model. Residual values will be examined for an approximate normal distribution. If residual values from the regression model have a skewed distribution then an appropriate transformation, truncation, or a nonparametric analysis based on ranks will be performed. Descriptive analyses (e.g., boxplots) stratified by donor diabetes status group will be given at baseline, 1 month, and 1 year.

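### The ECD model names recipient clustering only, although both corneas of a donor may be used; the passages on donor correlation disagree and should be reconciled (small effect if mates are few)

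*Combined protocol and SAP*

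**What the plan says.** - **Mates are allowed.** Section 8.3 states that "both eyes of the donor may be provided for the study" and leaves the sample size unadjusted for it. The reasons given are that the earlier preservation-time study had no failures among mates, a low failure rate and a "low number of cornea mates in the study". A similar pattern is expected here. No mate count or cap is given.
- **Status belongs to the donor.** The synopsis classifies diabetes from the donor's history or postmortem HbA1c.
- **ECD model.** Section 8.7 compares donor groups while "adjusting for baseline ECD, corneal diagnosis, and recipient study eyes (random effect"). Of the analysis set it says that "only participants with a gradable 1-year image who have not experienced graft failure 1-year after DMEK will be included in the analysis".
- **Primary model.** Section 8.6 uses a proportional hazards model with a frailty for participants who contribute two eyes. No donor term is named.
- **Donor provisions.** Section 8.3 offers a sensitivity analysis where there are "cases of graft failures occurring from cornea mates both assigned in the study, sensitivity analysis will account for the correlation in the models". In its paragraph on participants with two eyes it also says that "the primary analyses will adjust for these correlations".
- **Deferral.** Section 8.1 calls the chapter a summary. Section 8.5 leaves sensitivity analyses of both the primary and the secondary outcome to the SAP.

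**The concern.** Two corneas from one donor share age, diabetes history, HbA1c and skin markers, and they always sit on the same side of the comparison. A positive residual correlation between them therefore does not cancel in the group contrast. It raises the true variance, and a model that ignores it reports a standard error that is too small.

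The recipient effect cannot stand in for a donor effect. Section 3.2.1 requires "Preservation time ≤ 11 days", and section 2.3 says that "second eye surgery as part of the study can be performed between 7 days and 6 months (182 days") after the first. Mates can therefore share a recipient only when the second surgery falls 7 to 11 days after the first, and never when the donor has known diabetes.

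The failure-based trigger in section 8.3 does not help ECD either. The reasoning there concerns a rare binary event. ECD is continuous and is analysed only in surviving grafts, so two mates that both survive can be correlated without any failure to set off the analysis.

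ECD loss is one of the trial's stated objectives, and section 8.13 tests it without multiplicity adjustment. At stake is the honesty of its p-value and confidence interval.

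**Working it through.** **Inputs from the documents.** Two-sided type I error 5% and power 90%; 1278 eyes with complete follow-up out of 1420 (1278 / 0.90 = 1420); failure rates 4% and 9%; 2:1 allocation (all section 8.3). The plan gives no ECD variance, mate count or within-donor correlation, so there is no ECD figure to reproduce.

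**Assumed inputs.** f is the share of analysed eyes whose mate is also analysed. rho is the within-donor correlation left after the model's covariates. The lead case is f = 10%, since section 8.3 expects few mates. Because ECD is adjusted for baseline ECD, rho could be low, so low values are shown too.

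**Formulas.**
- Design effect: DE = 1 + f × rho
- Type I error = 2 × (1 − Φ(1.96 / √DE))
- Standard error shortfall = 1 − 1/√DE

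| f | rho | DE | SE too small by | Type I error |
|---|---|---|---|---|
| 10% | 0.05 | 1.005 | 0.2% | 5.1% |
| 10% | 0.1 | 1.01 | 0.5% | 5.1% |
| 10% | 0.2 | 1.02 | 1.0% | 5.2% |
| 10% | 0.5 | 1.05 | 2.4% | 5.6% |
| 40% | 0.5 | 1.20 | 8.7% | 7.4% |

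**After the ECD exclusions.** Mean failure is (2 × 4% + 9%) / 3 = 5.7%. With 90% followed, the share kept is 0.90 × 0.943 = 0.849, taking every image as gradable. Then f of 10% becomes 8.5% and the type I error for rho 0.2 to 0.5 is 5.2 to 5.5%. The upper case falls from 7.4% to 7.0%.

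**Simulation.** With 20,000 replicates, rejection at rho 0.3 and 0.5 was 5.7% and 6.3% for f = 20% (formula 5.7% and 6.2%), and 6.9% and 8.2% for f = 50% (formula 6.8% and 8.0%). A second simulation had 60,000 runs and a Monte Carlo error of 0.1 point. It used 1420 eyes of 1092 participants, an assumed recipient correlation of 0.3, and mates in different recipients. A recipient-only clustered variance rejected 5.2% and 5.7% at f = 10%, rho 0.2 and 0.5, and 7.7% at f = 40%, rho 0.5. A two-way donor and recipient variance rejected 5.0%, 5.1% and 5.2%. The second simulation compares groups at one time point and does not fit the repeated-measures model of section 8.7. At f = 10% its differences are not far above simulation noise.

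**How often the section 8.3 trigger fires.** At f = 10% there are 0.10 × 1278 / 2 ≈ 64 pairs, about 42.6 and 21.3 by group. The chance that both mates of a pair fail is p² + rho × p(1 − p).
- Read as both mates failing, at least one such pair occurs with probability 21% at rho 0. It is 34% at rho 0.05 and 44% at rho 0.1.
- Read as any failure in a pair, the probability at rho 0 is 1 − 0.96^85.2 × 0.91^42.6 = 99.9%.

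The wording does not settle which is meant.

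**Graft failure.** Starting from the nominal 90%, power = Φ((1.96 + 1.2816)/√DE − 1.96). With f = 10% and rho 0.05 to 0.1 this is 89.9 to 89.7%, and the type I error is 5.1%.

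**The case against.** The strongest reply is that the plan already covers this. Section 8.3 introduces the correlations as those of participants' eyes and of donors' eyes together, then says that "the primary analyses will adjust for these correlations". Section 8.12 speaks of the primary-analysis models for graft failure and ECD alike, and section 8.14 has its adjusted models for both outcomes follow the primary analyses. On that reading donor adjustment of ECD is promised in general terms and section 8.7 is only less detailed. This largely stands. A reader might infer that the plan ignores donor correlation altogether, or leaves clustering in the severity models open. The documents support neither. What remains is that the sentence sits among the remarks on two-eye participants, while the two sections that specify the models name recipients only.

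Second, the SAP may supply the detail. This also stands. The examples in section 8.5 (operative complications, recipient diabetes) do not mention donors, but they are only examples.

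Third, the effect is negligible. With few mates it is small. Section 8.3 writes 1420 eyes as about 947 and 473 donors, which fits roughly one eye per donor or loose wording. Adjustment for baseline ECD may absorb much of the shared donor variation.

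Fourth, a donor random effect crossed with the recipient effect would be poorly identified when nearly all donors contribute one eye. That is right, and it is why the robust variance comes first in the fix.

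**Conclusion.** The point holds as an inconsistency in the text with a modest consequence. Followed as written, section 8.7 gives ECD standard errors that are too small if mates are used and their residual correlation is positive. With few mates, as the protocol expects, the type I error moves from 5% to between 5.1% and 5.6%. The 7.4% figure needs mates to be common and strongly correlated, which goes against the protocol's own expectation, so it should not be read as the likely size. A reader might also infer that the graft-failure comparison is compromised. At f = 10% and rho 0.05 to 0.1 it is not: power stays within 0.3 points of nominal. Everything numerical rests on assumed f and rho. The change is worth making but optional, and confidence is medium because the separate SAP was not in the text reviewed.

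**What to change.** 1. In section 8.7, account for donor as well as recipient clustering regardless of observed failures. Use a two-way (donor and recipient) cluster-robust variance, with a crossed donor random effect as an optional check. The severity models in section 8.14 that mirror the primary analyses then follow the same rule.
2. Reconcile section 8.3 with sections 8.6 and 8.7 by saying which correlations each model handles. Run the donor-clustered sensitivity analysis of graft failure unconditionally.
3. Report the number of mate pairs by donor group, so that readers can see whether the expectation of few mates was met.

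The cost is protocol or SAP wording and some programming. Donors already receive study identifiers (section 7.4), so no new data are needed. ECD intervals would be about 1 to 2.5% wider at f = 10% and rho 0.2 to 0.5 (√1.02 = 1.010, √1.05 = 1.025). If the SAP already contains donor clustering, only the reconciliation of wording and the mate count remain.

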8.4 Outcome Measures

8.4.1 Primary Efficacy Endpoint

- Graft failure within 1 year of surgery as defined in the SAP

Graft failure will be assessed and defined as the occurrence of one of the following:

- Cornea which requires regrafting for any reason
- Recipient cornea remains cloudy after surgery without clearing for 8 weeks or longer

For eyes meeting the definition of graft failure above, the principal cause of graft failure will be classified and described in the SAP. Further, the date of graft failure will also be described in the SAP.

8.4.2 Secondary Endpoint

Endothelial cell density at 1 year is considered a secondary endpoint.

8.5 Analysis Dataset and Sensitivity Analyses

The primary analysis will follow the intent-to-treat principle, with the following exceptions: it will exclude eyes that did not have DMEK surgery, received a non-study donor cornea tissue, had an anterior chamber IOL implanted during surgery, or experienced a suprachoroidal hemorrhage. It is highly unlikely that any of these events could be related to diabetes status of the donor.

Safety outcomes will be reported for all enrolled study eyes that have DMEK surgery, irrespective of whether the participant completed the study.

Sensitivity analyses for the primary and secondary outcomes, such as adjusting for significant operative complications and/or recipient diabetes, will be described in the SAP.

8.6 Analysis of the Primary Efficacy Endpoint

Summary statistics (Kaplan-Meier estimates of 1-year graft failure with 95% confidence intervals) will be reported by donor diabetes status groups (with versus without diabetes). Further, point estimates and 95% confidence intervals for donor diabetes status group differences will be presented.

One-year graft failure between donor diabetes status groups will be compared using a proportional hazards model while adjusting for corneal diagnosis and accounting for participants who have two study eyes included in the study using a frailty model. The proportional hazards assumption will be tested. If this assumption is violated, then hazard ratios will be presented separately over time. There will be no imputation of missing data in the primary analysis.

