Sample Size	Up to 1420 completed surgeries (~947 donors without diabetes and ~473 donors with diabetes) with a goal of 1278 completing the 1-year follow-up
Treatment Groups	Study eyes will be assigned to receive either a cornea from a donor without diabetes or a cornea from a donor with diabetes. Assignment selection will use a minimization procedure which will prioritize assignments in a 2:1 distribution of tissue from donors without known diabetes to tissue from donors with known diabetes as determined by the eye bank. Participants with 2 study eyes cannot receive a cornea from a donor with known diabetes in both eyes. The minimization procedure will attempt to achieve balance on several factors, including the surgeon and whether the recipient had diabetes versus not.
Participant Duration	12 months follow-up after DMEK

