 - diabetic retinopathy with history of intravitreal anti-VEGF therapy

Once diabetes status and severity are determined a computer program will be able to run a minimization procedure to select a donor cornea for a given participant DMEK surgery. For the first eye of each participant, if only one donor cornea is available, then this cornea is selected. Otherwise, if all available donor corneas are the same donor diabetes classification, then a cornea is randomly selected from all available. Otherwise, if at least one donor cornea is from each donor diabetes classification, a minimization procedure will select based on achieving balance on several factors, including the surgeon, and the donor diabetes risk categorization score.

For participants with two study eyes, if the first eye received a cornea from a known diabetic donor, then the second eye will receive a cornea from a donor the eye bank determined as non-diabetic, if available. If a cornea from a donor the eye bank determined as non-diabetic is not available, then surgery must be postponed or performed outside of the study. If the first eye received a cornea from a donor the eye bank determined as non-diabetic, then the minimization procedure will run and the second eye could receive a cornea from a known diabetic or nondiabetic donor.

The most important aspect of the protocol for the eye banks is maintaining masking of the surgeon and surgeon staff from any direct or indirect knowledge of the diabetic status of the donor tissue assigned to study participants.

The surgeon will be masked to all other donor parameters except storage solution. NO eye bank's standard reports and labels (including donor tissue report, donor cornea container label, recipient information form, package insert form and adverse reaction report) **can be sent to the surgeon**. Study-specific documentation will be used in lieu of these reports. See the Eye Bank Manual of Procedures for a summary of the EBAA waivers and other references, and examples of the DEKS Donor Tissue Label, DEKS Donor Tissue Report, DEKS Adverse Reaction Report, and DEKS Shipping Label.

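### The primary Cox model omits surgeon, a minimisation factor, although tissue supply can set donor group for some first eyes: confounding is possible, probably small, and cheap to guard against by stratifying

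*Combined protocol and SAP*

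**What the plan says.** **Model.** Section 8.6 specifies donor group, corneal diagnosis and a frailty for two-eye participants ("while adjusting for corneal diagnosis and accounting for participants who have two study eyes included in the study using a frailty model"). It has no surgeon, site or eye-bank term.

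**Balancing factors.** The Protocol Summary (Treatment Groups) describes an attempt to achieve "balance on several factors, including the surgeon and whether the recipient had diabetes versus not". Section 3.2.2 says that "a minimization procedure will select based on achieving balance on several factors, including the surgeon, and the donor diabetes risk categorization score". Surgeon is the one factor named in both places.

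**When minimisation does not decide.** Section 3.2.2 has two supply rules for first eyes. The first covers a sole cornea: "For the first eye of each participant, if only one donor cornea is available, then this cornea is selected". The second covers stock of a single type: "if all available donor corneas are the same donor diabetes classification, then a cornea is randomly selected from all available". In either case the stock on hand fixes the donor group.

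**Second eyes.** After a diabetic first graft, the second is non-diabetic by rule. Otherwise: "If the first eye received a cornea from a donor the eye bank determined as non-diabetic, then the minimization procedure will run". Section 8.3 adds that, after a non-diabetic first graft, "there is a 1/3 chance that the second study eye will receive a cornea from a donor with known diabetes".

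**Context.** Section 8.3 lists diabetic donor shares from 24% to 36% and calls the differences regional. Section 4.1 leaves surgical technique unstandardised. Section 2.1 lets one surgeon contribute up to 20% of eyes. Section 8.5 gives recipient diabetes as an example of a sensitivity adjustment and leaves the detail to the SAP.

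**The concern.** The plan treats surgeon as important enough to balance on and then leaves it out of the primary analysis. Where minimisation runs, that omission mainly costs efficiency. Where supply decides, nothing balances donor group within surgeon at that assignment. If surgeons or sites with more diabetic tissue also have higher (or lower) failure, part of that difference is credited to donor diabetes. The direction is unknown.

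Reclassification of some donors on post-mortem HbA1c after surgery (Protocol Overview) adds to this: even perfect minimisation balances the assigned groups, not the analysed ones.

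Recipient diabetes is a different case. No route to confounding is shown for it. It belongs in the model only because the plan names it as a balancing factor.

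**Working it through.** **1. The plan's own figures.** With 30% of participants bilateral, 1092 × 1.30 = 1419.6, which matches "1092 participants would need to be enrolled in order to enroll 1420 study eyes". Evaluable eyes: 1278 / 0.90 = 1420. Expected events at 4% and 9% with 2:1 allocation: 852 × 0.04 + 426 × 0.09 = 72.4.

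**2. How many eyes supply can force.** Second eyes: 1420 − 1092 = 328, or 328 / 1420 = 23.1%. First eyes are 76.9%, so the supply rules as written can touch at most about 77% of eyes.

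**3. Set-up, with no true donor effect.**
- Let p be the share of first eyes that are supply-forced and s the local diabetic supply.
- First-eye diabetic share: a = p·s + (1 − p)/3.
- Second-eye diabetic share: (1 − a)/3.
- Overall share at a site type: 0.769a + 0.231(1 − a)/3.
- Assumed: half the eyes at low-supply sites with 3% failure, half at high-supply sites with 9%. Supply is 24% vs 34% or 24% vs 36%, taken from the shares in Section 8.3.

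**4. One case in full (p = 1, 24% vs 34%).**
- Diabetic shares are 24.31% and 31.23%.
- Failure in the diabetic group: (0.2431 × 3% + 0.3123 × 9%) / 0.5554 = 6.37%. In the non-diabetic group it is 5.86%. The spurious difference is 0.52 points.
- SE = √[0.06 × 0.94 × (1/355 + 1/923)] = 0.0148, so the shift is 0.35 SE.
- Two-sided type I error = P(Z > 1.96 − 0.35) + P(Z < −1.96 − 0.35) = 6.4%.

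**5. Range.**

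| Assumption | Spurious difference (points) | Type I error |
|---|---|---|
| All first eyes forced | 0.52–0.61 | 6.4–7.0% |
| Same, second eyes set at 1/3 diabetic | 0.55–0.65 | 6.7–7.4% |
| Half of first eyes forced | 0.25–0.30 | 5.3–5.5% |
| A quarter forced | 0.12–0.15 | 5.1% |
| All forced, failure 3% vs 6% | 0.26–0.31 | 5.5–5.7% |
| All forced, supply 24% vs 27% | about 0.16 | 5.1% |

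**6. Simulation with a shared-frailty Cox model.** Settings: 8000 runs per case, 983 participants, 1278 eyes, 30 unequal sites, gamma frailty variance 1 (assumed), no corneal-diagnosis term. Type I error, unadjusted then site-stratified (Monte Carlo SE about 0.3 points):
- nothing forced: 5.5%, 5.3%
- half of first eyes forced, 24/36%: 5.3%, 4.8%
- all forced, 24/34%: 6.3%, 4.9%
- all forced, 24/36%: 7.1%, 4.8%

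**7. Power cost at 4% vs 9%.**

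| Strata | Unstratified | Stratified | Strata with no events |
|---|---|---|---|
| 30 | 94.0% | 93.5% | 17% |
| 60 | 93.4% | 92.4% | 37% |
| 90 | 94.1% | 92.4% | 49% |

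The number of surgeons is not stated, so 60 and 90 are assumptions.

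**The case against.** The case against acting is fair in several respects.

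- **The visible inflation needs an extreme case.** With half of first eyes forced, the simulated unadjusted error cannot be told from that with nothing forced. Forcing every first eye means that minimisation never runs for one. It would give 355 or 364 diabetic grafts out of 1278, about 28%, against the planned third. It also allows no offset from later minimised assignments. This stands: it is an upper bound for this set-up, not an estimate.
- **The causal inputs are assumed.** The documents give no forced share, no between-surgeon failure variation and no link between supply and risk. The supply spread is itself soft: the 36% and 27% in Section 8.3 come from one supplier in adjacent periods, and these are donor-pool shares, not study tissue. This also stands.
- **The SAP may cover surgeon.** Sections 8.5, 8.12, 8.14 and 8.15.2 defer detail to it, and a surgeon sensitivity analysis may be there. That would not change the primary model, whose terms Section 8.6 states.
- **Sparse strata.** Information is lost from them, but the measured power cost is small.

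Stronger readings are tempting. A reader might infer that the primary result will be seriously biased. A separate log-rank simulation, without frailty or corneal diagnosis, does reach 9–18% type I error. But that takes a surgeon's diabetic share that tracks failure risk perfectly, with assumed spreads in both. At correlation 0.5 it gives 6.6–7.6%, and at zero 5.5–5.6%. Nothing in the documents supports a close link. A reader might also infer that the two descriptions of the minimisation contradict each other. Both lists are open-ended, so they do not.

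**Conclusion.** The point holds as a modest one. Surgeon is a declared balancing factor, it is absent from the primary model, and the assignment rules do not guarantee balance on it. Under the assumed 3% vs 9% site failure rates and the supply shares used, confounding reaches at most about 0.5–0.65 points against a 5-point design difference, with type I error 6.4–7.4%. It is close to nominal (5.1–5.5%) when a quarter to a half of first eyes are forced. That it is probably small is a judgement resting on those assumptions.

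The documents do not support saying that confounding is present, that it favours either donor group, or that leaving out recipient diabetes biases the comparison. The change is still worth making in advance: actual imbalance will be seen only as data accrue, and adding surgeon then would look post hoc.

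**What to change.** In Section 8.6 and the SAP:

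1. Prespecify one stratification of the primary Cox model: surgeon, with surgeons below a stated eye count pooled within their site. Keep corneal diagnosis and the participant frailty.
2. Add recipient diabetes as a covariate, using the status recorded at assignment and not the HbA1c-reclassified status of Section 2.4.1, because the assignment status is what was available to balance on.
3. Beside the Kaplan-Meier difference, report a one-year failure difference over the same strata with Mantel-Haenszel weights, so that strata with one donor group get zero weight.
4. Tabulate supply-forced assignments by donor group and site.

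The cost is wording; surgeon, site and recipient diabetes are already recorded. Expect to lose about 0.5–2 points of power, staying above the stated 90%, and some information from strata with no events or one donor group. Two limits apply. The power figures come from a model without corneal diagnosis, and the weighted difference was not simulated. Stratifying also does not remove differences among surgeons who are pooled, or eye-bank and calendar effects within a surgeon.
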